### ***Follow-up Assessment:***

After initial assessment, the catheter will be assessed by the research team every 24 +/- 5 hours as long as the patient is hospitalized up to 7 days or 168 hours. At each follow up interval the researcher notes the date/time of evaluation and assesses for any signs and symptoms of complications and functionality of the device. A catheter is functional if the IV flushes without resistance. Catheters will be assessed daily for signs and symptoms of complications. See Appendix C for details regarding the assessment for complications. Any signs or symptoms of complications or lack of functionality will be reported to the patient's primary care team so that management of the IV catheter can be addressed. If the catheter and adhesive are removed early due to catheter failure or complication, or for patient discharge prior to 7 days a medical adhesive remover may be used.

If the catheter was identified to have any signs or symptoms of complications during follow-up assessment the date and time of observation of the complication will be documented in the data collection tool and the primary team will be notified of the complication. If the catheter was removed prior to the follow-up assessment then the IV removal time and the reason for removal will be obtained through chart review. For all catheters removed due to a complication, re-insertion attempt data will be tracked through the medical record in the nursing section for venous lines and need for reinsertion of the IV or escalation to a midline, PICC, or CVC will be noted. If the patient is discharged prior to the time of follow-up assessment then the time of discharge will be documented and the IV will be presumed functional until time of discharge unless otherwise noted in the chart.

The medication administration record will be queried for all medications given through each catheter with specific attention to antibiotics and anticoagulants. Vesicants/irritants that are generally given via central line or considered caustic to the vessel will be noted in both groups. Number of doses will be recorded. See Appendix D for full list of non-neoplastic vesicants.

Additional data gathered by research staff on follow-up evaluation includes: dwell time in days/hours, hospital length of stay, and number of peripheral IVs for duration of stay.

Appendix E represents the data collection documentation tool for all catheter follow-ups.

## **Statistical Rationale and Analysis Plan:**

### ***Sample Size and Power Analysis***

For this randomly allocated two-groups experiment, the primary outcome is catheter survival associated with securement devices. Sample size calculation is based on primary outcome: composite or all cause premature removal due to complication of the IV catheter. Based on existing literature, the maximum mean failure rate across major investigations is 25% which functions as the estimated failure rate of the standard of care group. Assuming a minimum difference of 10% needed for prompting a change in practice and based on existing literature, the experimental group (standard of care plus tissue adhesive) is hypothesized to have a composite failure rate of 15%. 154 subjects per group for a total sample size of 308 subjects is the minimum recommendation assuming a 10% dropout rate. To account for a larger dropout percentage, 350 patients or 175 subjects per group is the final sample size to provide 80% power to detect a significant effect.

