**NCT04086693**

**6/16/2020**

# **Peripheral Intravenous Catheter Securement with Tissue Adhesive Compared to Conventional Dressing: A Randomized Controlled Trial**

## **Background/Scientific Rationale:**

Nearly all hospitalized patients require intravenous (IV) access for treatment. Patients rely on functional vascular access to receive life saving IV therapies. Generally, peripheral IVs have high failure rates with 19-25% of IVs failing prior to completion of therapy and 45-56% of ultrasound-guided peripheral IVs failing prior to completion of therapy. Dislodgment, infiltration/extravasation, and phlebitis are common complications that lead to early failure. IV restarts are a common procedure and are unfortunately simply a part of a normal workday for nurses. A failure rate of up to 56% in a technology that is over 75 years old is unacceptable.

If access is lost, patients may experience treatment delays, dissatisfaction from repeat needle-sticks, and health complications if the patient's condition becomes critical. IV failure can result in a number of negative health/quality outcomes including phlebitis and infections and/or skin necrosis from caustic medication infiltration; utilization of invasive procedures such as peripherally inserted central catheters (PICC) and central lines; and wasted medical/nursing time.

Because failure rate is high, it is important to approach insertions methodically to improve survival rates. One area of opportunity is securement of the catheter. Accidental dislodgment is a common cause of early IV failure accounting for up to 50% of catheter failures. Beyond dislodgment, inadequate fixation of the catheter to the patient's skin causes micromotion, leading to vein irritation and entry of skin bacteria into the entry site. This micromotion leads to phlebitis, occlusion, and infection. Standard practice for securement involves placement of a polyurethane dressing with clear tape. A variety of additional devices are available on the market including tissue adhesives, specially designed securement dressings, and sutureless securement devices. The evidence suggests the use of tissue adhesives may decrease peripheral IV failure with a decrease in dislodgments and occlusions compared to the alternatives. Bugden et al. found that skin glue reduced catheter dislodgment by 7% and reduced peripheral IV failure by 10%.

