While some evidence supports the use of tissue adhesives for securement, further randomized controlled trials are needed to assess the effectiveness of this intervention. Further, only one prospective, randomized trial evaluated patients in the emergency room setting. Nearly 50% of all hospital admissions start in the emergency department (ED) and 80% of hospitalized patients require IV access. This highlights the importance of understanding the impact of tissue adhesives on peripheral IV survival for patients admitted through the ED. While Bugden found that skin glue reduced IV failures for patients hospitalized from the

ED, patients were only followed for 48 hours. The general consensus is to continue using IVs as long as there is no clinical indication for removal. As the average hospital length of stay in the United States is 4-6 days, it is clear that the 48 hour cutoff is a critical flaw in the analysis and further investigation over a longer time period is urgently needed.

We propose a prospective randomized controlled trial to evaluate peripheral IV failure with ED patients that are hospitalized comparing securement with standard securement plus Adhezion Biomedical SecurePortIV™ to standard securement.

**Specific Aim 1:** Test the prediction that the experimental securement solution of standard dressing plus Adhezion Biomedical SecurePortIV™ will have a lower probability of failure compared to the control standard of care securement.

For Aim 1, an improved survival of the experimental securement solution will be evaluated by functionality of catheter for intravenous therapy prior to patient discharge. The event is failure of functionality identified during follow-up assessment during hospitalization. Duration of dwell and functional failure of the catheter will be employed to estimate catheter survival.

**Specific Aim 2:** Determine the difference in cause-specific IV failure rates between the experimental and control groups. Specific etiologies to be evaluated include dislodgment, infection, phlebitis, and occlusion.

**Specific Aim 3:** Determine the difference in costs associated with the experimental group versus the control group. Cost calculation will include all costs of placement in each group: labor and material.

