**Exclusion Criteria:**

1. Patients with ultrasound-guided IV insertions
2. Alternate site of cannulation
3. Voluntary withdrawal
4. Patients with a non-standard polyurethane dressing
5. Known allergy to cyanoacrylate or formaldehyde

The survival analysis will only be performed on patients that have an IV dwell time greater than 48 hours. Over 85% of patients admitted to a progressive floor have length of stay greater than 48 hours. The sample size calculation reflects an assumed 10 - 15% exclusion rate.

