### ***Statistical Analysis***

Characteristics of enrolled patients will be summarized using means [standard deviations] and medians [interquartile ranges] for continuous variables, and frequencies (percentages) for categorical variables. Exploratory data analyses including histograms, Pareto charts, scatter plots, and box plots will be further used to show the distribution. Appropriate transformations and estimation procedures will be performed as necessary. To test the effect of securement strategies on each of aims, we will further use Cox proportional hazard regression models for time-to-event outcomes and logistic regression models for binary outcomes. P-values of less than 0.05 will be considered statistically significant. Analysis will be conducted using SAS 9.4.

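### The 80% power claim gives no time window for its 25% and 15% failure rates, while the survival analysis as written counts only failures after 48 hours

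*Combined protocol and SAP*

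**What the plan says.** **Planning rates.** For controls, Sample Size and Power Analysis says that "the maximum mean failure rate across major investigations is 25% which functions as the estimated failure rate of the standard of care group". For the adhesive arm, "the experimental group (standard of care plus tissue adhesive) is hypothesized to have a composite failure rate of 15" per cent. The 10-point gap is justified in two ways: as the smallest difference that would change practice, and by existing literature. The final 350 patients (175 per group) "is the final sample size to provide 80% power to detect a significant effect". No time window is attached to either rate.

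**Where the figures seem to come from.** Background/Scientific Rationale reports "19-25% of IVs failing prior to completion of therapy", and the top of that range equals the planning rate. It also reports, from an emergency department trial, that "skin glue reduced catheter dislodgment by 7% and reduced peripheral IV failure by 10" per cent. Of that trial it says that "patients were only followed for 48 hours", which it treats as a critical flaw.

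**Who is analysed.** The paragraph closing the Exclusion Criteria says: "The survival analysis will only be performed on patients that have an IV dwell time greater than 48 hours". Under Initial Assessment, dwell starts when the new dressing is applied. The same closing paragraph gives a length-of-stay reason (over 85% of progressive-floor patients stay beyond 48 hours) and a 10–15% exclusion allowance. The form in Appendix E has a different rule: it removes patients discharged within 48 hours of insertion. Specific Aim 1 sets no 48-hour lower limit on the failure event, and follow-up runs to 168 hours.

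**The concern.** On the literal dwell rule, a catheter that fails at 20 hours has a dwell of 20 hours and leaves the survival analysis. Every analysed failure then falls after 48 hours. The planning rates do not describe that period: the control rate appears to count failures from insertion, and the cited adhesive effect comes from the first 48 hours alone. The power section neither mentions the restriction nor converts the rates.

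What is at stake is how the primary result is read. A null result might be taken as ruling out the 10-point benefit that the plan says would change practice. Yet under the plan's own rates and a constant hazard, a post-48-hour analysis would not expect a 10-point difference.

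**Working it through.** **Inputs.** 25% versus 15%, 80% power, 175 per group and 10% dropout (Sample Size and Power Analysis); 10–15% exclusion (Exclusion Criteria). The significance rule is "P-values of less than 0.05 will be considered statistically significant"; the plan does not say one- or two-sided, so two-sided is assumed.

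**Step 1: the plan's own figure.** The usual two-proportion formula is n = [1.96·√(2p̄(1−p̄)) + 0.84·√(p₁(1−p₁)+p₂(1−p₂))]² / (p₁−p₂)². With p₁ = 0.25, p₂ = 0.15 and p̄ = 0.20, n is 250 per group, or 250/0.9 = 278 with 10% dropout. The plan's 154 is not reproduced.

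**Step 2: power at the planned size, all failures counted.** Power = Φ{[|p₁−p₂| − 1.96·√(2p̄(1−p̄)/n)] / √([p₁(1−p₁)+p₂(1−p₂)]/n)}.

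- 175 per group: (0.100 − 0.0838)/0.0424 = 0.38, so power is 65%.
- After 10% exclusion (175 × 0.90 ≈ 158): 60%.
- After 15% exclusion (175 × 0.85 ≈ 149): 58%.

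**Step 3: rates among catheters that reach 48 hours.** The documents do not say what share of failures occurs early. As an illustration, assume constant hazards that give 25% and 15% by a horizon H. Take H from 96 to 168 hours, which spans the 4–6 day average stay in the Background (a general US figure) and the 168-hour follow-up cap. Then:

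- failure after 48 hours, given survival to 48 hours = 1 − (1−p)^((H−48)/H)
- share of control failures by 48 hours = (1 − 0.75^(48/H))/0.25

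| H (hours) | Control | Adhesive | Difference (points) | Control failures before 48 h | Power, 149 per group | Power, 250 per group |
|---|---|---|---|---|---|---|
| 96 | 13.4% | 7.8% | 5.6 | 54% | 35% | 53% |
| 120 | 15.9% | 9.3% | 6.6 | 43% | 40% | 60% |
| 144 | 17.5% | 10.3% | 7.2 | 37% | 43% | 64% |
| 168 | 18.6% | 11.0% | 7.6 | 32% | 46% | 67% |

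The last column separates this point from the sample-size arithmetic. At 250 per group, where 25% versus 15% does give 80%, the restricted analysis would have 53–67%.

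**Step 4: how many patients remain.** The 149 treats the 15% allowance as covering every exclusion. If it covers short stays only, as its stated reason suggests, early failures leave as well. From 148.75 per group:

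- H = 96: 148.75 × 0.75^0.5 ≈ 129 controls and 148.75 × 0.85^0.5 ≈ 137 adhesive patients; power 31.8%.
- H = 168: 148.75 × 0.75^(2/7) ≈ 137 and 148.75 × 0.85^(2/7) ≈ 142; power 43.5%.

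Total loss among controls would then be 22–26% (1 − 137/175 to 1 − 129/175), outside the plan's 10–15%.

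**Step 5: sensitivity to timing.** If 75% of the cumulative hazard fell before 48 hours, with the same hazard ratio (ln 0.85/ln 0.75 = 0.565), the later rates would be 6.9% versus 4.0% and power 18–19%.

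**The case against.** The strongest reply is that the plan never meant to drop early failures. The dwell sentence is followed at once by a length-of-stay reason, the 10–15% allowance fits short stays, and Appendix E removes early discharges only. On that reading early failures stay in and the rate mismatch largely disappears. This stands as a reading of intent. It does not remove the problem, because the only sentence that defines the survival analysis set does so by dwell, and the power section names no window. Even on this reading, power is about 58–60%.

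Four further points stand in part.

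- The link between the 25% and the whole-dwell range is inferred from matching figures; the power section gives no specific source.
- The 10 points is also a minimum worthwhile difference, so it is not purely a borrowed effect. The Background also cites other evidence favouring adhesives, without a figure.
- The restriction is stated for the survival analysis and not expressly for the logistic models under Statistical Analysis.
- Constant hazard and the 96–168 hour horizon are the reviewer's assumptions, so Step 3 illustrates and does not bound the answer.

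A reader might also infer that the adhesive's cited effect does not carry over beyond 48 hours. The documents do not show that: a trial that stopped at 48 hours is silent about later benefit.

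**Conclusion.** The point holds for the analysis as written: 80% power was claimed for rates with no stated window, and the dwell rule removes failures that those rates appear to include.

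The size depends on which rule is meant. With all failures from time zero counted and 25% versus 15% taken as assumptions for that window, power is about 65% at 175 per group, or 58–60% after exclusions. With the dwell rule kept, the illustration gives about 35–46% at 149 per group, or about 32–44% if early failures are lost on top of a 15% length-of-stay exclusion, and less if failures cluster early. All figures assume a two-sided 5% test.

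Two stronger readings should be avoided. One is that the window alone explains the shortfall: the planned size falls short of 80% even for 25% versus 15% over the full period, so correcting the window alone would not restore it. The other is that the trial's power simply is 35–46%: that figure rests on the literal dwell rule and on a hazard shape that the documents do not give.

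**What to change.** 1. Reconcile the dwell rule in the Exclusion Criteria with the discharge rule in Appendix E, including the clock each uses (new dressing versus insertion).
2. In Sample Size and Power Analysis, state the window to which 25% and 15% apply, make it the window analysed, and restate the power at 350 patients.
3. The simplest route is to count all failures from time zero to 168 hours, declare 25% and 15% as planning assumptions for that window, and state power of about 65% at 175 per group, or 58–60% at 149–158 per group.
4. If the dwell rule is kept, replace 25% and 15% with rates conditional on reaching 48 hours. State the assumed timing of failures and whether early failures come out of the 10–15% allowance or on top of it, and give the resulting power as a range.
5. Say that the cited 10-point effect was observed only over 0–48 hours and that its size afterwards is unknown.

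The cost is protocol and SAP wording plus a short recalculation. No extra patients are requested. The downside is a less favourable stated power.

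### The stated 80% power does not follow from the plan's own 25% vs 15% at p < 0.05; 175 per group gives about 65% two-sided and at most 77% on the most favourable one-sided reading.

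*Combined protocol and SAP*

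**What the plan says.** Under Sample Size and Power Analysis, the control rate is taken from the literature ("the maximum mean failure rate across major investigations is 25" per cent) and the experimental rate is hypothesised to be 15%. The 10-point gap is given a practical meaning: "Assuming a minimum difference of 10% needed for prompting a change in practice". Two sample sizes follow. The first is a minimum: "154 subjects per group for a total sample size of 308 subjects is the minimum recommendation assuming a 10% dropout rate". The second allows for larger dropout: "350 patients or 175 subjects per group is the final sample size to provide 80% power to detect a significant effect".

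That section gives no significance level, sidedness or formula. The level appears under Statistical Analysis: "P-values of less than 0.05 will be considered statistically significant". Sidedness appears nowhere, although Specific Aim 1 is directional: the experimental securement "will have a lower probability of failure compared to the control standard of care securement".

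The closing paragraph of Exclusion Criteria adds two relevant statements: "The sample size calculation reflects an assumed 10 - 15% exclusion rate", and "The survival analysis will only be performed on patients that have an IV dwell time greater than 48 hours".

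**The concern.** For 25% vs 15%, the usual requirement at two-sided 0.05 and 80% power is about 250 evaluable patients per group. The plan's minimum of 154 already includes 10% dropout, so it implies only about 139 evaluable per group. The final 175 is also far below 250 before any loss is taken off.

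Readers will use the power statement to judge the result. If the trial finds no significant difference, the plan says that a 10-point benefit had only a 20% chance of being missed. If the true chance is nearer 35-42%, a useful device could be dismissed on evidence weaker than the plan claims.

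**Working it through.** **Inputs.** p1 = 0.25, p2 = 0.15 and 80% power (Sample Size and Power Analysis); significance level 0.05 (Statistical Analysis); 1:1 allocation (Initial Assessment); loss of 10-15% (Sample Size and Power Analysis; Exclusion Criteria). Sidedness is an assumption, so both readings are shown.

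**1. Attempt to reproduce the plan's figures.** 154 × 0.90 = 138.6, or about 139 evaluable per group. The two-proportion formula with pooled variance under the null is

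n = [z_α √(2p̄(1−p̄)) + z_β √(p1(1−p1) + p2(1−p2))]² / (p1−p2)², with p̄ = 0.20.

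- Two-sided: [1.960 × √0.32 + 0.842 × √0.315]² / 0.01 = (1.1087 + 0.4724)² / 0.01 = 249.98, so **250** per group. With loss: 250/0.90 = 278; 250/0.85 = 295 (both rounded up).
- One-sided 0.05: (0.9305 + 0.4724)² / 0.01 = 196.8, so **197** per group. With loss: 197/0.90 = 219; 197/0.85 = 232.
- Other two-sided versions: unpooled 248, arcsine 248, continuity-corrected 270. One-sided: 195, 196 and 217.

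None of these gives 139, 154 or 175.

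**2. Power at the planned size.** Power = Φ{[0.10 √n − z_α √0.32] / √0.315}. At n = 175, two-sided: (1.3229 − 1.1087)/0.5612 = 0.382, and Φ(0.382) = 0.649. The rows with loss assume that patients are lost at random and the failure rates stay the same.

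| Evaluable per group | Two-sided (exact) | One-sided 0.05 (exact) |
|---|---|---|
| 175 (no loss) | 0.649 (0.654) | 0.758 (0.761) |
| 157 (10% loss) | 0.601 (0.607) | 0.717 (0.720) |
| 149 (15% loss) | 0.579 (0.583) | 0.697 (0.699) |

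The exact values come from enumerating the pooled z-test over the two binomial distributions. At the stated minimum, two-sided power is 0.593 with all 154 evaluable and 0.550 with 139.

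**3. Time-to-event basis.** The plan names Cox models, so this was checked too. Under proportional hazards, HR = ln 0.85 / ln 0.75 = 0.565 and ln HR = −0.571. Schoenfeld events = 4(z_α + z_β)² / (ln HR)²: 97 two-sided, 76 one-sided. At an assumed average cumulative failure of 20%, 350 patients give 350 × 0.20 = 70 events.

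Power = Φ(|ln HR| √d / 2 − z_α). With d = 70: Φ(2.389 − 1.960) = 0.666 two-sided and Φ(2.389 − 1.645) = 0.772 one-sided. With 10% or 15% loss (63 or 59.5 events), it is 0.620 or 0.596 two-sided and 0.733 or 0.711 one-sided.

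**4. What 80% would require at 175 per group.**
- Solving for the level: z_α = (1.3229 − 0.4724)/√0.32 = 1.504, a two-sided level of about 0.13.
- Solving for the effect at two-sided 0.05: the experimental rate would have to be 13.3% against 25%. With 157 or 149 evaluable it would be 12.7% or 12.4%.

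**5. Precision.** With both rates near 20%, the 95% CI half-width for the difference is 1.96 √(2 × 0.2 × 0.8 / n): 8.4 points at 175, 8.8 at 157 and 9.1 at 149. At 175 per group, an observed difference must be below about 10 − 8.4 = 1.6 points for the interval to exclude 10. A non-significant difference between about 1.6 and 8.4 points would leave 10 open.

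**The case against.** The strongest objection is that the fault may be an unstated significance level, not wrong arithmetic. The sizing paragraph gives no level, and the 0.05 comes from the analysis section. A log-rank calculation with HR 0.565, 20% average failure, 80% power and one-sided 0.10 needs 55.3 events, or 55.3/0.40 = 138.2 per group; 138.2/0.90 = 153.6, which rounds up to the stated 154. At one-sided 0.10, two-proportion power at 175 per group is 86%. This may be how the figure arose, or it may be coincidence: 25% vs 12% at two-sided 0.05 also needs 139 per group. Either way, one-sided 0.10 contradicts the plan's p < 0.05, so the 80% claim fails for the test that the plan says it will use.

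Three further points have some force:

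- **Sidedness.** The 65% rests on an assumed two-sided test, and Aim 1 is directional. At one-sided 0.05 the shortfall without losses is only about 3-4 points (76-77%), but 175 was chosen to absorb dropout. After 10-15% loss, one-sided power is 70-72% on the two-proportion basis.
- **Loss.** The restriction to dwell time over 48 hours is related to the outcome, so random loss with unchanged rates is an approximation. The 58-60% is conditional on it; the 65% is not.
- **Interval wording.** The Cox and logistic models named in the plan yield hazard and odds ratios. Interpreting a null result through an interval for the risk difference would add an estimate that the plan does not define.

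**Conclusion.** The concern holds. At p < 0.05 with 25% vs 15%, none of the standard calculations tried reaches 80% power with 175 per group. The best case, at 77%, needs a one-sided test, proportional hazards, 20% average failure and no losses at all. Under the usual two-sided reading, power is 65% with no losses and about 58-60% after 10-15% random loss. The chance of missing the plan's minimum worthwhile difference is then 35-42%, against the 20% implied (24-30% on the one-sided two-proportion reading). The minimum of 154 per group is unsupported on the same inputs. The conclusion does not depend on sidedness; only the size of the shortfall does. Type I error is unaffected. This must be corrected because the stated power is wrong for the very difference on which the plan rests a change in practice.

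**What to change.** In Sample Size and Power Analysis, state the significance level, sidedness and method, and replace the power sentence. For a two-sided test: 'With 175 per group, power for 25% vs 15% at two-sided 0.05 is about 65% (about 58-60% if 10-15% are not evaluable, assuming random loss and unchanged rates); 80% power is available for 25% vs about 12-13%.' If the sponsor intends a one-sided 0.05 test, it should say so and give 76% (70-72% after loss). Delete the 154/308 minimum. If event counts are quoted (about 70 expected, about 97 needed two-sided), label them as assuming 20% average cumulative failure and proportional hazards.

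A useful addition is: 'A non-significant result will be interpreted by whether the 95% confidence interval for the difference excludes the 10-point difference.' This requires a risk-difference estimate to be defined; the power correction does not depend on it.

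The power correction changes one paragraph and makes the claim less favourable. It needs no extra patients, visits or data. For information only, keeping 80% power for 10 points two-sided would take 250 evaluable per group (278 enrolled with 10% loss, 295 with 15%).
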